**OBJECTIVES**

*To test the efficacy of an e-Health intervention for increasing HIV-negative or HIV-unknown YMSM's successful uptake of HIV and STI testing willingness (e.g., routine HIV/STI testing) and PrEP awareness and willingness, as compared to the attention-control condition over a 12-month period.*

*To examine the quality of HIV test counseling and PrEP-related referrals to YMSM within local HIV/STI testing sites in 3 cities (Houston, Philadelphia, and Atlanta) through the use of mystery shoppers*

*Qualitatively assess testing sites' satisfaction with the biannual performance assessments and their improvements in service delivery when working with YMSM across the three regions.*

Study Design or Schema

Per the diagram above, the study is a two-arm randomized controlled trial. Once participants are proven eligible and they have provided informed consent, they will be randomized to one of two arms: intervention (Get Connected) and control (site locator portion of Get Connected). Participants randomized to the control condition will only have access to the site locator portion of Get Connected, with information on HIV prevention services. Participants randomized to the intervention condition will receive tailored online content specific to their demographic characteristics (e.g., age, race/ethnicity, location, and relationship status), HIV/STI risk behaviors (e.g., HIV/STI testing history; substance use; communication with partners regarding status), and sociocultural context (e.g., homelessness, incarceration). Five study assessments (surveys) are conducted at months 1, 3, 6, 9, and 12 for a total of 12 months follow-up for each arm.

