- *Intervention Acceptability:* At each follow-up, YMSM will report data on the acceptability of their assigned arm. We will also use the Systems Usability Scale to ascertain participants' overall satisfaction with the intervention, perception of the information quality, and perceived usefulness of their intervention to improve their health.
- *Use of Intervention over time:* We will measure intervention exposure using paradata

(e.g., process data emerging from use of the WebApp) from backend database of the intervention website, including counts of user sessions, session lengths, pages visited, and functions utilized. This information will assist in examining whether intervention dosage influences the overall efficacy of the intervention, and inform the cost analysis and wider implementation and scalability.

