## **10.0 STATISTICAL/ANALYTIC CONSIDERATIONS**

### **10.1 Introduction**

10.1.1 We will test the efficacy of GC in increasing HIV-negative or HIV-unknown YMSM's successful uptake of HIV and STI testing (e.g., routine HIV/STI testing) and increase in PrEP awareness and willingness, as compared to the attention-control condition over a 12-month period. Descriptive statistics of the psychosocial and demographic characteristics of the participants will be described for all and by intervention group. These will be compared between treatment groups using t-tests or Wilcoxon rank sum tests for continuous variables and chi-square tests for categorical variables. To test for intervention efficacy, we will conduct primary

analyses of our primary outcomes using regression analyses to compare our treatment group to the control using the appropriate link function (identity for continuous outcome, logit for binary outcome, and natural log for count outcomes). The regression will be run with group assignment only in the model, as well as, controlling for participants' socio-demographic characteristics, ATOD and psychological distress, and intervention-related process data (e.g., frequency of use, acceptability). Interactions between group assignment and these characteristics will be tested to explore potential moderators of treatment effect. We will repeat these analyses for the secondary outcomes (e.g., theoretical mediators)).

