10.3.2 As a secondary analysis, we will build on our GLMM framework to examine whether the intervention effects in the theoretical mediators (e.g., intentions, self-efficacy, perceived barriers) are associated with our outcomes. We will also test whether these relationships vary as a function of YMSM's varying engagement with the intervention (intervention acceptability; use of intervention over time). Interactions between group assignment and these characteristics will test for potential moderators of treatment effect.

10.3.3 For the qualitative interviews of agency directors, initial reading and coding of the transcripts will be reviewed, compared, and refined in team meetings. This systematic process will lead to the creation of a coding structure that includes a hierarchical set of constructs seen in the data. We will analyze several transcripts jointly to establish inter-coder reliability. The team will then code all transcripts using our coding structure and add inductive codes throughout the iterative analysis process. Throughout, we will discuss emerging themes, resolve difficulties or concerns that may arise while coding, and adapt the codebook as necessary. Since we were seeking to gain a multi-level understanding of the structural, organizational, and interpersonal barriers and facilitators of implementing GC, our analysis will utilize a phenomenological framework. Although our analysis will rely primarily on a phenomenological inductive approach, we will also employ aspects of deductive analysis that take into account our guiding conceptual framework. This combination of analytic strategies will allow us to conduct a phenomenological analysis (inductive) that was initially informed by existing research and theory via the conceptual framework (deductive). We will analyze the qualitative data using thematic analysis until we have reached saturation.

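### The arm-by-use and arm-by-acceptability interactions in 10.1.1 and 10.3.2 do not estimate a causal dosage effect, and can create or hide one; the intention-to-treat result is unaffected

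*Combined protocol and SAP*

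**What the plan says.** Section 6.1.2 (Use of Intervention over time) collects backend data on the WebApp, "including counts of user sessions, session lengths, pages visited, and functions utilized", and states the purpose: "This information will assist in examining whether intervention dosage influences the overall efficacy of the intervention". The same section has participants rate the acceptability of their own arm at each follow-up.

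Section 10.1.1 runs the efficacy regressions with group alone and then with further terms, among them "intervention-related process data (e.g., frequency of use, acceptability", and adds: "Interactions between group assignment and these characteristics will be tested to explore potential moderators of treatment effect".

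Section 10.3.2, labelled secondary, asks whether the relationships between mediators and outcomes depend on participants' "varying engagement with the intervention (intervention acceptability; use of intervention over time". Its next sentence is: "Interactions between group assignment and these characteristics will test for potential moderators of treatment effect".

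On what each arm can use, the Study Abstract (Study Design or Schema) says: "Participants randomized to the control condition will only have access to the site locator portion of Get Connected". The GC arm also has the tailored What, Why and How sections (3.1), which are re-tailored after every follow-up survey (5.4.1).

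The order in 5.1 is consent, randomisation, baseline survey, then access to the WebApp. No number of sessions is assigned in either arm. The plan does not define a use measure that is comparable between arms, gives no method for self-selected use, and does not say that the result is non-causal.

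**The concern.** A moderator test has a clear meaning when the variable describes the participant before assignment. Use and acceptability do not, for two reasons.

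- They are chosen or reported after randomisation. A man already inclined to test may both use the site more and test more, whatever the site does.
- They refer to different content. One session in the control arm is time on a site list. One session in the GC arm may be time on tailored content that controls cannot receive at any level of use. Acceptability has the same problem, since each arm rates its own version.

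The interaction therefore compares two use–outcome slopes, each of which may reflect motivation to a different degree. If they differ, a dosage effect can appear where GC does nothing. If they differ the other way, a real one can be masked. What is at stake is any statement in the trial report that more use of GC gives more, or no more, benefit.

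**Working it through.** The plan gives no figure for this analysis, so there is none to reproduce. The check asks what the planned interaction does when GC has no effect at all.

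**Inputs from the documents.** 400 participants and a two-sided 0.05 level (10.2.1), with 1:1 allocation (5.3), so 200 per arm.

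**Assumed inputs.** Motivation M is standard normal and raises the log-odds of testing by b per SD; b = 0.8 is the main case, an odds ratio of exp(0.8) = 2.23. About 30% test. Standardised use U has correlation rGC with M in the GC arm and rC in the control arm. Arm has no effect on testing.

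**Model fitted.** logit P(tested) = γ0 + γ1·arm + γ2·U + γ3·arm×U, with a Wald test of γ3.

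**Expected result.** To a first approximation the slope of testing on use in each arm is b times that arm's correlation, so the false interaction odds ratio is about exp{b(rGC − rC)}. For rGC = 0.5 and rC = 0.1 this is exp(0.8 × 0.4) = exp(0.32) = 1.38.

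**Simulated result**, 2,000 trials per row, b = 0.8:

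| rGC | rC | exp{b(rGC − rC)} | Mean interaction OR | Interaction significant | Intention-to-treat test significant |
|---|---|---|---|---|---|
| 0.5 | 0.5 | 1.00 | 1.00 | 4.7% | 4.6% |
| 0.5 | 0.3 | 1.17 | 1.17 | 10.2% | 4.2% |
| 0.5 | 0.1 | 1.38 | 1.36 | 26.8% | 4.6% |
| 0.5 | 0 | 1.49 | 1.46 | 37.5% | 4.5% |
| 0.2 | 0.5 | 0.79 | 0.79 | 17.8% | 6.0% |

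Two runs at rGC = 0.5 and rC = 0.25 gave 13.1% and 13.3%.

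**Sensitivity.**
- Strength of motivation: for b = 0.5, 0.8 and 1.2, rejection is 7%, 10% and 15% at rC = 0.3, and 19%, 38% and 60% at rC = 0. In the reversed case (last row of the table) it is 10%, 18% and 28%.
- Testing rate and size, at rGC = 0.5, rC = 0.1, b = 0.8: 18% if 15% test, 29% if 50% test, and 30% with 240 per arm.
- Scale of use: with raw session counts and equal correlations of 0.5, means of 6 v 2 or 10 v 2 (GC v control) give 12–16% at b = 0.8 and 14–26% at b = 1.2, with the interaction OR below 1 (0.90 to 0.94). Equal means of 4 give 5–6%.

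**The case against.** **The error may be nominal.** If use follows motivation equally in both arms and on the same scale, the test rejects at about 5%. This stands. The 38% needs control use to be unrelated to motivation, which is hard to defend when control use consists of looking up testing sites. The documents give no data on either correlation.

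**Section 10.3.2 is ambiguous.** The sentence before the quoted one concerns mediator–outcome relationships, there is no formula, and 6.1.2 does not point to 10.3.2. That these interactions are meant to answer the dosage question is therefore an inference. Section 10.1.1 is more direct: it names frequency of use and acceptability and then plans interactions with group.

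**The arms share content.** The control locator is a portion of the GC site, not an unrelated product. This is correct, but the tailored content is still unavailable to controls. Nor do the documents say outright that use is recorded in the control arm. If it is not, or is set to zero, the interaction cannot be estimated, which does not help the plan.

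**The simulation is simpler than the plan.** It uses one logistic model rather than the mixed-model framework of 10.3. It shows the mechanism and does not forecast an error rate.

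**Cost and scale-up.** A reader might infer that the interaction result will drive the cost analysis and wider roll-out. The documents do not support that: 6.1.2 says that the usage data themselves will inform those.

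**Conclusion.** The point holds as a limit on interpretation of a secondary, exploratory analysis. The planned interactions are not a causal dosage effect, and the bias has no fixed direction. Under the stated assumptions, with no GC effect, false significance ranges from nominal (equal correlations, same scale) through 13% (control correlation 0.25) to 38% (control correlation 0). The sign reverses when use tracks motivation more closely in the control arm, or when raw session counts differ between arms. The correlations and the strength of motivation are assumptions.

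Two stronger readings should be resisted. One is that the plan will tend to report a false benefit of dose; masking a true one is also possible. The other is that the efficacy conclusion is compromised. The primary analysis in 2.4 is by assigned arm and its model contains neither use nor acceptability; in the simulations the intention-to-treat test stayed at 4–6% throughout.

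**What to change.** 1. In both 10.1.1 and 10.3.2, limit interaction tests for moderation to characteristics that pre-date randomisation. The baseline survey follows randomisation but precedes WebApp access (5.1), so name the baseline values of such characteristics explicitly.

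2. Report use and acceptability by arm, labelled descriptive and non-causal. The label matters: in the simulation with no GC effect (b = 0.8, rGC = 0.5), GC participants above median use tested at 36% and those below at 24%. That split is only an illustration; the plan does not propose it.

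3. If an exposure effect is wanted, add an optional sensitivity analysis: a complier average causal effect with randomised arm as instrument, equal to (tested proportion in GC − tested proportion in control) ÷ (proportion of the GC arm exposed), with a bootstrap interval.
   - Define exposure in advance as opening any GC content that controls cannot reach. Include the ranked Where listing if it differs from the control locator, because 3.1 counts directing users to good agencies as part of the GC effect; leaving it out would threaten the exclusion assumption.
   - State that assumption, and state that the estimate is for any versus no exposure, not for dose-response. Staff help participants into the WebApp at baseline (5.1), so exposure may be near complete and the estimate close to intention-to-treat; no exposure figure is given.

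The cost is SAP wording and, if chosen, one analysis of data already planned for collection. The trial gives up any causal dose-response claim, and the complier estimate is less precise and depends on its assumptions.

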#### 10.4 Missing Data

Several procedures will be used to conduct data analysis when data for either outcomes or covariates are missing. The first step will be to assess the extent and pattern of missing data. If data are missing for only a few cases, then data analysis will be conducted only on study participants with complete data. However, when such a strategy would result in loss of data from a substantial proportion of participants, or if this approach would lead to biased or inaccurate results, then some form of imputation will be performed. The form of imputation used will depend on the nature of the data that are missing. For example, data that are collected repeatedly might be imputed using the "last value carried forward" method; and in some instances, interpolation between neighboring points might also be used.

When the primary endpoint is missing, one data analysis will be conducted using only cases with the endpoint. Subsequent analysis will be done where missing endpoints are imputed. Hot-deck imputation or regression imputation may also be used in this context.

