### 2.4 Study Hypotheses/Research Questions

- *Relative to the control condition, YMSM exposed to the GC intervention will report significantly greater increases in routine HIV/STI testing over a 12-month period. HIV testing will be the primary outcome for the trial.*
- *Relative to the control condition, YMSM exposed to the GC intervention will report increases in motivation around HIV testing (conceptualized as HIV/STI testing intentions, self-efficacy to engage in HIV/STI testing, and overcoming testing-related barriers).*
- *Relative to the control condition, YMSM exposed to the GC intervention will report significantly greater PrEP awareness and willingness to use PrEP).*

The primary analyses of the data from the Get Connected 2-parallel group randomized clinical trial will be performed according to the participants' original treatment assignment (i.e., intention-

to-treat analyses) and the inclusion of all data from all participants randomized in the final analysis.

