The primary assessment for a difference between intervention arms for 'frequent tester' rates will be a two-sided Z-test for independent proportions with pooled variance. Confidence intervals (95%) will also be reported for the observed difference between the GC and control arms in 'frequent tester' rates. The same analysis plan described above will be used for the other primary outcomes that as binary (i.e., STI testing, PrEP awareness).

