## 5.4 Intervention/Investigation Procedures

### 5.4.1 Get Connected Intervention

Participants will complete a 30- to 45-minute baseline survey that includes questions on lifetime HIV testing history, lifetime STI testing history and knowledge about STIs, date of their most recent STI test (if known), and whether they were ever diagnosed with an STI. GC will use baseline survey data to select and deliver personalized, tailored content to YMSM assigned to the intervention. Furthermore, as part of the participant's baseline visit, study staff will collect contact information where participants may be reached for follow-up assessments. We will use best practices to retain participants (e.g., collecting participant's cell phone number, email address, Facebook, WhatsApp, and/or Skype username, and contact information for 2 peers who could help us contact them). Additional surveys will occur at 1, 3, 6, 9, and 12 months after intervention initiation, and can be completed online. These follow-up surveys will repeat many of the questions from the baseline survey and will also include additional questions on HIV and STI testing in each 3-month period, including test results. These surveys will be the same for participants in the control and intervention arms. For participants in the intervention arm, the GC WebApp will be retailored after each follow-up survey, based on any different information provided on key questions.

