### 6.1.2 On-study Evaluations/Measures

- *HIV Testing:* Follow-up surveys will repeat the HIV testing questions in each follow-up survey. The HIV testing outcome will be: the proportion of MSM tested for HIV two or more times at least 3 months apart in the 12-month follow-up period (“frequent tester”). As an additional analysis, we will also examine the proportions of participants who receive one HIV test.
  - Among self-reported newly diagnosed HIV+ cases, we will measure their linkage and engagement with appropriate medical care after initial diagnosis using criteria employed in prior ATN protocols with youth. We will define linkage as an HIV-related medical visit within 45 days of referral, and engagement as a second HIV-related medical visit within 16 weeks of initial visit. Onset of ART initiation, self-reported adherence to ART, and viral suppression are exploratory indicators, as we recognize that our follow-up period may not be a sufficient amount of time to see these changes.
- *STI Testing:* The STI testing outcome is defined as the proportion of YMSM tested for STIs at least once in the 12-month follow-up period. We will ask participants what STIs they have been tested for, the anatomic sites where they were tested, the date of their most recent STI test (if known), and whether a medical provider had diagnosed them with an STI. In the follow-up surveys, we will ask participants whether they had been tested for STIs in the past 3 months (for the 1-month follow-up survey, we ask about the past 30 days). If STI testing is reported, we will ask participants to indicate what tests they received, and whether they were diagnosed with an STI by a medical provider.
- *PrEP Use:* At each follow-up assessment, PrEP-eligible HIV-negative YMSM (per CDC guidelines) will be asked whether they have begun using PrEP. We will also ascertain if a provider recommended PrEP and/or were offered a prescription for PrEP.
 

*Site Evaluations:* Across both trial arms, YMSM who report testing in the prior 3 months will complete self-evaluation forms of their testing experiences to assess comfort, quality, and concerns after visiting a site for HIV/STI testing and PrEP prevention services. The assessment form is the same form used by the mystery shoppers. We will use these data to update the WebApp and to send aggregate data of YMSM's satisfaction with services to agencies biannually.

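### The supplementary analysis with imputed primary endpoints (section 10.4) has no rule for imputation uncertainty or for arm, so its error rate and effect estimate depend on which permitted fill is used

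*Combined protocol and SAP*

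**What the plan says.** Section 10.4 begins with a general rule for missing outcomes or covariates. If few cases are affected, complete cases are analysed. Otherwise some imputation is used, in a form chosen after the extent and pattern of missingness have been examined. It adds that "data that are collected repeatedly might be imputed using the" last-value-carried-forward method, and mentions interpolation.

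For a missing primary endpoint, "one data analysis will be conducted using only cases with the endpoint". Then: "Subsequent analysis will be done where missing endpoints are imputed". And: "Hot-deck imputation or regression imputation may also be used in this context". The number of fills, the variance rule, the donor pool and the role of arm are not stated there or elsewhere.

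Related text:
- Section 2.4 promises "the inclusion of all data from all participants randomized in the final analysis" and compares frequent-tester rates with a "two-sided Z-test for independent proportions with pooled variance".
- Section 6.1.2 defines the HIV endpoint as "the proportion of MSM tested for HIV two or more times at least 3 months apart in the 12-month follow-up period", and the STI endpoint as at least one test over the same period.
- Section 10.3.1 adds a logistic regression of at least one HIV test over follow-up.
- Section 5.4.1 says the follow-up surveys "will also include additional questions on HIV and STI testing in each 3-month period, including test results".

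**The concern.** These endpoints are aggregated over 12 months, with one value per person. For the frequent-tester Z-test, the imputed analysis is the only stated way to include everyone randomised. A single fill analysed as if it had been observed would comply with the text.

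Three faults can follow. Filling within arm leaves the estimate unbiased but understates its variance. Filling without regard to arm pulls the arms together. Carrying a 3-month report forward misclassifies people. A carried 'yes' can supply a second HIV test that nobody reported, and a carried 'no' can miss later testing.

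Because the method is to be chosen after the missing data have been looked at, a disagreement with the observed-case result could be purely technical.

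**Working it through.** **Inputs from the documents.** 240 per arm (5.3); two-sided 0.05, 80% power, 400 participants, 13 points, within-person correlation 0.25 or 0.75 (10.2); 20% attrition (3.1, Phase 1c), so 192 observed and 48 missing per arm; about 400 of 480 retained (3.3), which is 16.7% attrition; more than 90% retention in other studies (8.2).

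**Assumed.** Frequent-tester rate 20-35%; dropout completely random and equal by arm.

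**1. The plan's own figure.** No control rate is stated. With 25% vs 38% and pooled variance, n per arm = [1.96√(2×0.315×0.685) + 0.8416√(0.1875+0.2356)]² / 0.13² = 1.835² / 0.0169, about 200. That is 400 in total, so the stated size is reproduced.

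**2. Closed form, within-arm single fill of every dropout.** With n = 240, r = 192, m = 48, the true variance divided by the variance the Z-test assumes is:
- random hot-deck: n/r + m/n = 1.25 + 0.20 = 1.45
- fractional predicted value with uninformative predictors: n/r = 1.25

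Type I error = 2[1 − Φ(1.96/√ratio)], which gives 10.4% and 8.0%. At 16.7% attrition the hot-deck ratio is 240/200 + 40/240 = 1.367, giving 9.4%.

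**3. Simulation.** Four quarterly reports per person; frequent tester taken as 'yes' in at least two; dropouts observed for 0 to 3 windows; 40,000 trials per setting. An endpoint is undetermined if it is neither already met nor out of reach. At 20% attrition this holds for 14-16% of participants.

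| Within-arm single fill, 20% attrition | Type I error |
|---|---|
| Hot-deck, every dropout | 10.3-10.7% |
| Hot-deck, undetermined only | 8.5-9.4% |
| Hot-deck matched on earlier reports | 6.8-8.3% |
| Fractional regression on earlier reports | 6.0-7.0% |

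A smaller simulation (4,000 trials) with a different person-effect model gave 8.4-8.6% for matched hot-deck and 6.9% for regression, so the ends of these ranges are approximate. Most-likely-category fills lie outside them. Without predictors they give 4.0-4.6% at rates of 10-40% and about 50% at a rate of 50%. From earlier reports they give 7.0-7.5% (correlation 0.25) or 5.2-5.6% (0.75).

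Every-dropout hot-deck gives 9.2-9.6% at 16.7% attrition and 7.4-7.7% at 10%. For the at-least-one-STI-test endpoint (50% rate assumed, 20% attrition) it gives 10.2-10.4%, or 8.3-8.9% for undetermined only.

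**4. Arm-blind hot-deck.** Both arms receive the same expected fill, so 13 points becomes 13 × 192/240 = 10.4. At 25% vs 38%:

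| Arm-blind fill | Effect read | Power |
|---|---|---|
| Every dropout | 10.4 | 69% |
| Undetermined only | 11.2-11.5 | 75-77% |
| Matched on earlier reports | 11.7-12.3 | 78-83% |
| Completers only, for comparison | 13.0 | 79% |

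Type I error stays near 5% throughout.

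**5. Carry-forward.** Type I error is 4.9-5.1%. Among undetermined dropouts with at least one report, a carried 'yes' is a false frequent tester in 36-46% (correlation 0.25) or 14-17% (0.75). A carried 'no' misses a true one in 10-19% or 4-8%. For at-least-once endpoints a carried 'yes' is harmless.

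**6. Multiple imputation of per-survey reports within arm.** With 20 sets and Rubin's rules: error 4.9-5.2%, effect 13.0, power 82-84%. Baseline history, city and test timing were not simulated.

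**The case against.** The strongest reply is that the observed-case analysis comes first, the imputed one is supplementary, the list of methods is permissive, and hot-deck or regression can be run multiply with a proper variance. All of that stands. The excess error arises only if one fill is made and its uncertainty ignored. A reader might infer that the trial's frequent-tester result carries 10% type I error. The documents do not support that: under completely random missingness the observed-case Z-test held 4.6-5.3%.

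A reader might also infer that every fill fails whichever way arm is handled. That is too strong. The 10.4% figure needs every dropout overwritten by a random completer, although 10.4 speaks of missing endpoints and some dropouts' endpoints are already known. An arm-blind deck matched on earlier reports loses only about a point of effect and little or no power against completers.

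In the other direction, a reader might infer that the repeated-measures models are exempt. Section 10.4's general rule covers any missing outcome and suggests carry-forward for repeated data, so carried reports could enter the GEE in 2.4 and the GLMM in 10.3.1. Those models are unaffected only if fitted to observed reports.

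Finally, random dropout is an idealisation. Section 8.4 discontinues participants who report an HIV-positive diagnosis, which is missingness caused by testing, and says interview data from those who withdraw are destroyed. Multiple imputation under missing at random does not resolve either.

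**Conclusion.** The concern holds as under-specification of a supplementary analysis. At 20% attrition, compliant within-arm single hot-deck or fractional-regression fills put type I error between about 6% and 10.4%, depending on which endpoints are filled and how donors are matched; most-likely-category fills can fall outside that. Arm-blind hot-deck keeps the error near 5% and reads 13 points as about 10.4 to 12. Carry-forward keeps the error near 5% but misclassifies individuals.

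The sizes rest on assumed event rates, completely random dropout equal by arm, and a four-window proxy for the 3-month spacing. The hot-deck and fractional-fill error rates change little with the event rate. The inner ends of the ranges depend on how well earlier reports predict later testing, which the documents do not give. The change is worth making before data are seen, but it does not put the observed-case test in doubt.

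**What to change.** For frequent tester, any STI test and tested-at-least-once HIV, replace the methods in 10.4 with multiple imputation of the per-survey testing reports:
- Include test timing, so that the 3-month spacing can be derived.
- Impute within arm or with an arm term, using observed reports, baseline testing history and city. State the number of sets.
- Derive the endpoint in each set and combine with Rubin's rules.

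Also:
- Rule out carry-forward, interpolation and single fills for testing outcomes, and fit the GEE and GLMM to observed reports.
- Define which cases have the endpoint so that inclusion does not depend on the outcome, for example completers of the 12-month survey. In simulation, using all known endpoints read 13.0 points as 13.3.
- State how the endpoint is classified for participants discontinued after reporting an HIV-positive diagnosis, rather than imputing their later tests as missing at random.
- Reconcile the destruction of withdrawn participants' interview data (8.4) with the inclusion of everyone randomised (2.4).
- A delta-shifted sensitivity analysis is optional.

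The cost is SAP wording and modest programming. Simulated 95% interval widths at 25% vs 38% and 20% attrition were 17.1-17.6 points for multiple imputation, 16.4 for a single within-arm hot-deck and 18.4 for completers. Intervals are therefore wider than after a single fill but, in that simulation, narrower than for completers.
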